6.5.2.3 Missing Doses

All efforts should be made to administer IP on all of the scheduled days of each 28-day treatment cycle. Patients who have a dose interruption due to toxicity at any point in the first 12 months of treatment may resume treatment with their assigned IP and complete the 12-month treatment period. Any missed doses during that period should not be added after the last scheduled day of administration to compensate for missed doses.

7. RESTRICTIONS DURING THE STUDY AND CONCOMITANT TREATMENT(S)

7.1 Restrictions during the study

The following restrictions apply while the patient is receiving study treatment and for the specified times before and after:

Females of childbearing potential who are sexually active with a non-sterilized male partner must use at least one highly effective method of contraception (Table 4) from the time of screening and must agree to continue using such precautions for 180 days after the last dose of study drug; cessation of birth control after this point should be discussed with a responsible physician. Periodic abstinence, the rhythm method, and the withdrawal method are not acceptable methods of birth control. Male partners of a female subject must use male condom plus spermicide throughout this period.

 Females of childbearing potential are defined as those who are not surgically sterile (ie, bilateral tubal ligation, bilateral oophorectomy, or complete

hysterectomy) or post-menopausal (defined 12 months with no menses without an alternative medical cause).

Non-sterilized males who are sexually active with a female partner of childbearing potential must use male condom plus spermicide from screening through 180 days after receipt of the final dose of study drug. Female partners of a male subject must use a highly effective method of contraception throughout this period.

Highly effective methods of contraception are described in Table 4. A highly effective method of contraception is defined as one that results in a low failure rate (i.e. less than 1% per year) when used consistently and correctly. Note that some contraception methods are not considered highly effective (e.g. male or female condom with or without spermicide; female cap, diaphragm, or sponge with or without spermicide; non-copper containing intrauterine device; progestogen-only oral hormonal contraceptive pills where inhibition of ovulation is not the primary mode of action [excluding Cerazette/desogestrel which is considered highly effective]; and triphasic combined oral contraceptive pills).

Restrictions relating to concomitant medications are described in Section 7.2.

Table 7 Highly Effective^a Methods of Contraception

Barrier/Intrauterine Methods	Hormonal Methods	
Copper T intrauterine device Levonorgesterel-releasing intrauterine	Etonogestrel implants: e.g. Implanon or Norplan	
system (eg, Mirena®)b	 Intravaginal device: e.g. ethinylestradiol and etonogestrel 	
	 Medroxyprogesterone injection: e.g. Depo-Provera 	
	 Normal and low dose combined oral contraceptive pill 	
	 Norelgestromin/ethinylestradiol transdermal system 	
	• Cerazette (desogestrel)	

Table 7 Highly Effective Methods of Contraception

- ^a Highly effective (i.e. failure rate of <1% per year)
- b This is also considered a hormonal method

Blood donation

Subjects should not donate blood while participating in this study, or for at least 90 days following the last infusion of durvalumab (MEDI4736) or tremelimumab or 28 days following the last dose of azacitidine or decitabine, whichever is the longest time period.

7.2 Concomitant treatment(s)

The Principal Investigator must be informed as soon as possible about any medication taken from the time of screening until the end of the clinical phase of the study (final study visit). Any concomitant medication(s), including herbal preparations, taken during the study will be recorded in the CRF.

Restricted, prohibited, and permitted concomitant medications are described in the following tables. Refer to Section 6.6 for guidance on management of IP-related toxicities.

7.2.1 Permitted concomitant medications

Investigators may prescribe concomitant medications or treatments (e.g., acetaminophen, diphenhydramine) deemed necessary to provide adequate prophylactic or supportive care except for those medications identified as "excluded" as listed in Section 7.2.2.

Antiemetics are not required during the study; however, at the Investigator's discretion, subjects may receive prophylactic antiemetics approximately 30 minutes prior to each dose of azacitidine or decitabine.

Treatment with antidiarrheal medications should be prescribed at the first sign of diarrhea. Premedication with antidiarrheal medication for subsequent doses of azacitidine or decitabine may be appropriate at the Investigator's discretion.

7.2.2 Excluded Concomitant Medications

The following medications are considered exclusionary during the study.

- 1. Any investigational anticancer therapy other than the protocol specified therapies
- 2. Any concurrent chemotherapy, radiotherapy (except palliative radiotherapy), immunotherapy, biologic or hormonal therapy for cancer treatment, other than any stated combination regimens. Concurrent use of hormones for non cancer-related conditions (e.g., insulin for diabetes and hormone replacement therapy) is acceptable. NOTE: Local treatment of isolated non-target lesions for palliative intent is acceptable (e.g., by local surgery or radiotherapy)
- 3. Any decitabine, or other demethylating or histone deacetylating agents.
- 4. Immunosuppressive medications including, but not limited to systemic corticosteroids at doses not exceeding 10 mg/day of prednisone or equivalent, methotrexate, azathioprine, and TNF-α blockers. Use of immunosuppressive medications for the management of investigational product-related AEs or in subjects with contrast allergies is acceptable. In addition, use of inhaled and intranasal corticosteroids is permitted. A temporary period of steroids will be allowed for different indications, at the discretion of the principal investigator (e.g., chronic obstructive pulmonary disease, radiation, nausea, etc).
- 5. Live attenuated vaccines within 30 days of durvalumab (MEDI4736) and tremelimumab dosing (ie, 30 days prior to the first dose, during treatment with durvalumab (MEDI4736) and tremelimumab for 30 days post discontinuation of durvalumab (MEDI4736) and tremelimumab. Inactivated vaccines, such as the injectable influenza vaccine, are permitted.
- 6. Drugs known to be metabolized by CDA (eg, cytarabine, gemcitabine, azacitidine, vidarabine, zalcitabine, zidovudine, telbivudine, didanosine, stavudine, lamivudine, abacavir, emtricitabine, entecavir, apricitabine, idoxuridine, trifluridine, tenofovir, and adefovir) should not be administered on the same days with cedazuridine or ASTX727.

Date 09202024

Table 8. Prohibited and Rescue Medications

Prohibited medication/class of drug:	Usage:		
Additional investigational anticancer therapy concurrent with those under investigation in this study	Should not be given whilst the patient is on IP treatment		
mAbs against CTLA-4, PD-1, or PD-L1	Should not be given whilst the patient is on IP treatment through 90 days after the last dose of IP.		
Any concurrent chemotherapy, local therapy (except palliative radiotherapy for non-target lesions, eg, radiotherapy, surgery, radiofrequency ablation), biologic therapy, or hormonal therapy for cancer treatment	hormones for non-cancer-related conditions		
Immunosuppressive medications, including, but not limited to, systemic corticosteroids at doses exceeding 10 mg/day of prednisone or its equivalent, methotrexate, azathioprine, and tumor necrosis factor α blockers	treatment (including SoC). (Use of immunosuppressive medications for the management		
Live attenuated vaccines	Should not be given through 30 days after the last dose of IP (including SoC) during the study		

Rescue/supportive medication/class of drug:	Usage:	
Concomitant medications or treatments (eg, acetaminophen or diphenhydramine) deemed necessary by the Investigator to provide adequate prophylactic or supportive care, except for those medications identified as "prohibited" as listed above		
Best supportive care (including antibiotics, nutritional support, growth factor support, correction of metabolic disorders, optimal symptom control, and pain management [including palliative radiotherapy, etc])		

Drug Substance Azacitidine/Decitabine (ASTX727)

Study Code 15-11430

Edition Number 13.0

Date 09202024

Rescue/supportive medication/class of drug:	Usage:
Best supportive care (including antibiotics, nutritional support, growth factor support, correction of metabolic disorders, optimal symptom control, and pain management	
[including palliative radiotherapy, etc])	

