Investigational Drug Durvalumab (MEDI4736)

Substance(s)

Azacitidine/Decitabine

(ASTX727)

Study Number

15-11430

Version Number

13.0

Date

09/20/2024

A Phase Ib Rescue Study With Oral Decitabine (ASTX727) and Durvalumab (MEDI4736) Combination Therapy in Recurrent and/or Metastatic SCCHN Subjects Who Have Progressed on Anti-PD-1, Anti-PD-L1, and/or Anti-CTLA-4 Therapy

IND Sponsor: [name], PhD

1

SCHEDULE OF STUDY ASSESSMENTS

Schedule of study assessments: Screening and Treatment Period (13 months: maximum of 13 doses, last infusion week 48, last dose week 46)

		All assessments to be performed pre-infusion unless stated otherwise				rwise	
Assessments to be performed at the times stipulated in the table and as clinically required in the management of the subject.	Screening*		Every 2 weeks	Every 4 weeks	Every 8 weeks	Every 12 weeks	
Day	-28 to -1*	1	Day 1 of the week	1	-1		
Week	-4 to -1	0	2, 4, 6, 8, 10, 12, etc.	4, 8, 12, 16, 20 etc.	, 8, 16, 24, 32 40, 48	, 12, 24, 36, 48	
			(±5 days)		(±7 days)	(±7 days)	
Written informed consent/assignment of subject identification number	X						
Demography and history of tobacco and alcohol use	X						
Previous treatments for head and neck cancer	X						
Inclusion/Exclusion criteria	X						
Medical ^a and surgical history	X						
Urine hCG or serum βhCG ^b	X	X		X			
Durvalumab (MEDI4736) administration				X t, u			
Tremelimumab administration				X ^{c, t, u}			
Oral decitabine (ASTX 727) or Azacitidine		X ^d		X ^{d, u}			
Physical examination ^e	X	X		X			

Schedule of study assessments: Screening and Treatment Period (13 months: maximum of 13 doses, last infusion week 48, last dose week 46)

		All asses	sments to be performed	pre-infusion unles	ss stated other	wise
Assessments to be performed at the times stipulated in the table and as clinically required in the management of the subject.	Screening*	Baseline	Every 2 weeks	Every 4 weeks	Every 8 weeks	Every 12 weeks
Day	-28 to -1*	1	Day 1 of the week		1	
Week	-4 to -1	0	2, 4, 6, 8, 10, 12, etc.	4, 8, 12, 16, 20, etc.	8, 16, 24, 32, 40, 48	12, 24, 36, 48
			(±5 days)		(±7 days)	
Vital signs (pre-, during and post- infusion vital signs assessments) ^f	X	X		X		
Weight	X	X		X		
Electrocardiogramg	x	X then as clinically indicated				
Adverse event/serious adverse event assessment	X^{h}	X	All visits			
Concomitant medications	X	X	All visits	All visits		
Palliative radiotherapy	As clinically	y indicated	1			
ECOG performance status	X	X		X		

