of the lesion is not safely accessible for biopsy, as determined by the treating physician. The on-treatment biopsy will be performed at the time of confirmed PR on imaging, as outlined above. For the non-superficial lesions, the on-treatment core needle biopsy will be performed under image guidance, either CT, MRI, or ultrasound. For dermal lesions, a core needle, excisional, or punch biopsy can be performed without image guidance. Biopsies will be obtained of lesion(s) which have decreased in size. A biopsy of a progressing lesion can also be obtained at the same time based on the discretion of the physician performing the procedure and the Investigator. Any biopsied lesion(s) can no longer be included in the objective tumor response assessment except for those patients whom only have one target lesion which is greater than 2 cm in diameter in any one direction. A post-treatment biopsy will be obtained in those patients who stop study treatment prior to completing 12 months of therapy or any patients who completes 12 months of therapy but did not undergo an on-treatment biopsy. Patients who had an on-treatment biopsy may undergo a post-treatment biopsy at the time of completing 12 months of therapy; however, this is not a mandatory biopsy. Any patient who restarts treatment will require another biopsy prior to restarting treatment. The fresh tumor biopsy sample will be shipped to and stored in the laboratory of [name] for analysis. At a minimum, 3 core biopsies will be obtained and 1 core will be formalin fixed and the other 1-2 cores will be flash frozen. Analyses which will be conducted include, but are not limited to, LINE-1 methylation, PD-L1 expression, tumor mutation analysis, RNA analysis, and MHC Class I/II and CD8+ T cell immunohistochemistry. After the clinical study report has been finalized, any retaining tissue will be retained for future research.

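### The protocol does not consistently say which lesions may receive palliative local treatment on study, and has no response rule for a target lesion that is irradiated or resected

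*Combined protocol and SAP*

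**What the plan says.** Five places in the protocol bear on palliative local treatment.

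- Section 7.2.2, item 2, main clause, excludes "Any concurrent chemotherapy, radiotherapy (except palliative radiotherapy), immunotherapy, biologic or hormonal therapy for cancer treatment". The exception in parentheses is not limited to any type of lesion.
- The NOTE that closes the same item reads "Local treatment of isolated non-target lesions for palliative intent is acceptable (e.g., by local surgery or radiotherapy".
- The prohibited part of Table 8 lists "local therapy (except palliative radiotherapy for non-target lesions, eg, radiotherapy, surgery, radiofrequency ablation" among the treatments that should not be given.
- The rescue and supportive part of Table 8 includes, under best supportive care, "optimal symptom control, and pain management [including palliative radiotherapy, etc". No lesion type is named. The carve-out for prohibited items is written on the row for other concomitant medications, not on this one.
- The schedule of study assessments and the follow-up schedules in Appendices 2 and 3 each carry a "Palliative radiotherapy" row, to be used when clinically indicated, again with no lesion type.

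On response, Section 9 derives every efficacy endpoint by program under RECIST 1.1. The one rule that removes a locally manipulated lesion is in Section 8.3.3.2: "Any biopsied lesion(s) can no longer be included in the objective tumor response assessment", with an exception for a patient whose only target lesion exceeds 2 cm. Nothing comparable exists for a lesion that is irradiated or resected.

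**The concern.** Two sites following the same protocol could treat the same patient differently and each point to a passage in support. For a painful target lesion, one could rely on the main clause of item 2 or on the best-supportive-care row, the other on the NOTE or the prohibited row. For palliative surgery of a non-target lesion, the NOTE and the prohibited row point in opposite directions.

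The statistical consequence follows from Section 9. If a target lesion is irradiated, whether under the permissive reading or as a deviation, its later measurements stay in the target sum. Local shrinkage from radiotherapy can then be recorded as response to ASTX727 plus durvalumab. Response status also has a use beyond description: Sections 3.1 and 5.1.3 bar continuation and retreatment for certain patients who progress after a confirmed response in target lesions.

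**Working it through.** The plan gives no figure on this point, so the check is a comparison of texts followed by one illustration.

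**Step 1. The passages side by side**

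| Place | Lesion limit on palliative radiotherapy | Palliative surgery |
|---|---|---|
| 7.2.2 item 2, main clause | none stated | not named |
| 7.2.2 item 2, NOTE | describes isolated non-target lesions; does not say that only these qualify | accepted for isolated non-target lesions |
| Table 8, prohibited row | non-target lesions only | prohibited, on the likelier parse |
| Table 8, best supportive care row | none stated | not named |
| Schedule of assessments, Appendices 2 and 3 | none stated | not named |

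On the parse: the examples in the prohibited row stand inside the parenthesis that states the exception. Surgery and radiofrequency ablation are not forms of radiotherapy, so they read more naturally as examples of the prohibited local therapy than of the exempted radiotherapy.

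**Step 2. What follows from the text**

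- Target lesions: two places point to non-target lesions and three set no limit. Irradiation of a target is not consistently barred.
- Surgery of a non-target lesion: accepted by the NOTE and prohibited by Table 8. Reading the NOTE as a limit on radiotherapy does not remove this conflict.
- The disagreement is not simply Section 7.2.2 against Table 8. Each contains both an unrestricted and a restricted statement.

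**Step 3. How shrinkage would enter response**

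Inputs: derivation under RECIST 1.1 (Section 9); at least one measurable lesion for entry (Section 4.1, item 8); confirmation at the next scheduled visit and not before 4 weeks (Sections 3.1 and 9.1.1). The protocol cites RECIST 1.1 without printing its thresholds; the calculation assumes that a partial response needs a fall of at least 30% in the target sum.

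Let w be the irradiated lesion's share of the baseline sum and s its fractional shrinkage, with the other targets unchanged. The change in the sum is −w × s.

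- Two targets of 30 and 20 mm, with the 30 mm lesion irradiated and falling to 15 mm: w = 30/50 = 0.60, s = 15/30 = 0.50, change = −0.60 × 0.50 = −0.30. Equivalently, (15 + 20)/(30 + 20) − 1 = 35/50 − 1 = −30%.
- A single target: w = 1, so s = 0.30 is enough.
- If w is below 0.30, even complete disappearance of the irradiated lesion cannot reach −30% on its own.

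The 30 and 20 mm example is chosen to meet the threshold exactly. It shows the mechanism, not its frequency. Confirmation at least 4 weeks later would not separate the causes if the shrinkage persists.

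**Step 4. Interaction with the biopsy rule**

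If the irradiated 30 mm lesion were also biopsied, Section 8.3.3.2 would take it out of response assessment and the example would not arise. The exposure is therefore to irradiated targets that are not biopsied, and to a sole target above 2 cm, which stays in the assessment even after biopsy.

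**The case against.** The strongest reply is that the protocol's intent is clear enough. Both passages that address lesion type point to non-target lesions. If the parenthesis in item 2 already allowed radiotherapy anywhere, naming radiotherapy in the NOTE would add nothing, so the NOTE is best read as narrowing it. The best-supportive-care and schedule rows are generic mentions, and Section 7.2.1 makes supportive care subject to the exclusions in Section 7.2.2. In the copy available, the Usage cells beside the relevant Table 8 rows are incomplete or blank, so a qualifier there cannot be ruled out. The schedules give palliative radiotherapy its own row, so affected patients should be identifiable at analysis.

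Much of this stands. A reader might infer that Section 7.2.2 freely permits irradiation of target lesions; the documents do not support that, because the NOTE sits inside the same item. What the reply does not settle is that the NOTE says such treatment is acceptable without saying only, that three places carry no qualifier, and that the surgery conflict survives either reading of the NOTE. It also leaves open how an irradiated target is scored if one occurs. Being able to identify those patients is not the same as having a rule for them.

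A reader might also infer that dose selection is at risk, because an irradiated lesion could supply the week-8 sample. The documents give no size or direction for any effect of radiotherapy on LINE-1 methylation or CD8+ infiltration, so they do not support a claim about the biologically effective dose or a rule excluding such samples.

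**Conclusion.** The concern holds as a drafting inconsistency together with a gap in the response derivation. A target lesion irradiated on study is not consistently barred, and if it happens, following the plan as written could credit its shrinkage as a response.

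The reach is limited. Section 2 makes the biologically effective dose the primary objective and safety the secondary one; response and progression are neither. No response-based rule governs escalation, expansion or the sample size. Beyond the descriptive response and progression data, what can be affected is the bar on continuation and retreatment after confirmed target-lesion response (Sections 3.1 and 5.1.3).

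The size per affected patient can be one spurious partial response, given the assumed 30% criterion, an irradiated lesion that makes up enough of the target sum, and shrinkage that lasts to confirmation. The documents do not say how often palliative radiotherapy is expected or how often it would involve a target, so no trial-level figure is given. Which clinical rule is right is not judged here.

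**What to change.** 1. Reconcile Section 7.2.2 item 2, its NOTE, both parts of Table 8, and the radiotherapy rows in the schedule of assessments and Appendices 2 and 3, so that they state one rule on which lesions may be treated locally and by what means. The content of that rule is for the sponsor.
2. Add to Section 9: if a target lesion is irradiated or resected on study, later assessments cannot contribute a new CR or PR and are treated as not evaluable for response, while progression elsewhere still counts. This is useful whichever clinical rule is chosen, because it also covers deviations.

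The cost is protocol wording and one derivation rule. The downside is that a few assessments become non-evaluable for response, including some in which the drugs may truly have contributed to the shrinkage.

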4.2 Exclusion criteria

Subjects should not enter the study if any of the following exclusion criteria are fulfilled:

- 1. Involvement in the planning and/or conduct of the study (applies to AstraZeneca staff and/or staff at the study site)
- 2. Histologically confirmed squamous cell carcinoma of any other primary anatomic location in the head and neck (eg. paranasal cavity) and non-squamous histologies (eg. nasopharynx or salivary gland)
- 3. History of another primary malignancy except for:
 - Malignancy treated with curative intent and with no known active disease ≥5 years before the first dose of study drug and of low potential risk for recurrence
 - Adequately treated non-melanoma skin cancer or lentigo maligna without evidence of disease
 - Adequately treated carcinoma in situ without evidence of disease eg, cervical cancer in situ
- 4. Receipt of the last dose of anti-cancer therapy (chemotherapy, immunotherapy, endocrine therapy, targeted therapy, biologic therapy, tumor embolization, monoclonal antibodies, other investigational agent) ≤ 21days prior to the first dose of study drug
- 5. Current or prior use of immunosuppressive medication within 28 days before the first dose of durvalumab (MEDI4736) or tremelimumab, with the exceptions of intranasal and inhaled corticosteroids or systemic corticosteroids at physiological doses, which are not to exceed 10 mg/day of prednisone, or an equivalent corticosteroid

Drug Substance Azacitidine/Decitabine (ASTX727)

Study Code 15-11430

Edition Number 13.0

Date 09202024

- 6. Any unresolved toxicity NCI CTCAE grade 2 from previous anti-cancer therapy with the exception of alopecia, vitiligo, and the laboratory values defined in the inclusion criteria.
 - Patients with Grade ≥ 2 neuropathy will be evaluated on a case-by-case basis and may be included after consultation with the Study Physician.
 - Patients with irreversible toxicity not reasonably expected to be exacerbated by treatment with their assigned IP (eg, hearing loss) may be included after consultation with the Study Physician.
- 7. Any prior Grade ≥3 immune-related adverse event (irAE) while receiving any previous immunotherapy agent, or any unresolved irAE >Grade 1
- 8. Abnormal coagulation parameters (PT > 15 secondss, PTT > 40 seconds, and/or INR > 1.5)

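### Section 7.2.2 item 4 excludes low-dose systemic steroids where Table 8 of the same section prohibits only doses above 10 mg/day

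*Combined protocol and SAP*

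**What the plan says.** Section 7.2.2 opens by stating that the medications it lists are excluded during the study. Item 4 covers immunosuppressives. It gives a non-exhaustive list that includes "systemic corticosteroids at doses not exceeding 10 mg/day of prednisone or equivalent", followed by methotrexate, azathioprine and TNF-α blockers.

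Table 8, also in Section 7.2.2, sets out prohibited medications. Its immunosuppressive row has the same companion drugs and the same non-exhaustive form, but names "systemic corticosteroids at doses exceeding 10 mg/day of prednisone or its equivalent".

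Item 4 carries several exceptions:

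- "Use of immunosuppressive medications for the management of investigational product-related AEs or in subjects with contrast allergies is acceptable".
- Inhaled and intranasal steroids are permitted.
- "A temporary period of steroids will be allowed for different indications, at the discretion of the principal investigator".

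Item 2 of the same list adds that "Concurrent use of hormones for non cancer-related conditions (e.g., insulin for diabetes and hormone replacement therapy) is acceptable".

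Two other places use the 10 mg/day figure. Exclusion criterion 5 in Section 4.2 bars immunosuppressives in the 28 days before the first durvalumab or tremelimumab dose, but excepts "systemic corticosteroids at physiological doses, which are not to exceed 10 mg/day of prednisone, or an equivalent corticosteroid". Appendix 1 allows patients with endocrinopathies who need continued steroid replacement to resume study drug if prednisone is at or below 10 mg/day, among other conditions.

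Two sentences direct the investigator to these rules. Section 7.2 says "Restricted, prohibited, and permitted concomitant medications are described in the following tables". Section 7.2.1 permits concomitant treatment "deemed necessary to provide adequate prophylactic or supportive care except for those medications identified as" excluded in Section 7.2.2.

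**The concern.** Item 4 and the Table 8 row are evidently two statements of one rule, and the threshold is reversed between them. Taken literally, item 4 singles out the least immunosuppressive doses for exclusion, in a list that otherwise names potent immunosuppressives.

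What is at stake is concomitant-medication handling. Take a patient who enters the study on stable low-dose prednisone for an unrelated condition, as criterion 5 allows. An investigator following item 4 could stop the steroid or record a protocol deviation; one following Table 8 would do neither. The documents state neither consequence, and the discontinuation list in Section 4.3 does not name steroid use, so these are plausible actions and not prescribed ones.

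**Working it through.** No arithmetic applies, and the plan has no figure to reproduce. The check is to set every statement of the 10 mg/day threshold side by side.

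| Place | What it governs | Up to and including 10 mg/day | Above 10 mg/day |
|---|---|---|---|
| Section 7.2.2, item 4 | On-study exclusion | Excluded by name | Excluded only through the non-exhaustive wording |
| Section 7.2.2, Table 8 | On-study prohibition | Not named as prohibited | Prohibited by name |
| Section 4.2, criterion 5 | Eligibility, 28 days before first durvalumab or tremelimumab dose | Allowed, at physiological doses | Not allowed |
| Appendix 1, endocrinopathies | Resuming study drug on replacement steroid | Allowed, with other conditions | Condition not met |

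**Which entries truly conflict.** Only item 4 and Table 8 govern the same thing at the same time, so there is one direct conflict. Criterion 5 is an entry rule; it shows what was intended, but is not a second contradiction. Appendix 1 runs in Table 8's direction and does not contradict item 4, because item 4 itself permits steroids for adverse events related to the study products.

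**Range of doses in conflict.** It covers doses above 0 and up to and including 10 mg/day. Above 10 mg/day the two texts agree: Table 8 prohibits those doses expressly, and item 4 reaches them because its list is not exhaustive.

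**Who is left after the exceptions.** From all systemic steroid use at 10 mg/day or less, remove:

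1. treatment of product-related adverse events (item 4);
2. contrast allergy (item 4);
3. a temporary course at the principal investigator's discretion (item 4);
4. arguably, hormone replacement (item 2).

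What remains is sustained, non-replacement use for an unrelated condition. Such patients can be enrolled: criterion 5 admits the dose, and criterion 9 does not exclude autoimmune disease that is readily managed with treatment and not at risk of serious exacerbation. The documents do not allow their number to be estimated.

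**Which text governs.** Section 7.2.1 sends the reader to Section 7.2.2, which contains both item 4 and Table 8. Section 7.2 sends the reader to the tables. Neither sentence says that one prevails over the other.

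**Test of the proposed change.** With *not* deleted, item 4 names doses above 10 mg/day. All four rows of the table then run in the same direction.

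**The case against.** The best opposing case accepts the error and disputes its weight.

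- **The conflict is partly inferred.** Table 8's list is also non-exhaustive, so it does not expressly permit low doses. That is true as a matter of form. But a stated threshold would have no purpose if doses below it were also prohibited, so the natural reading stands.
- **Table 8 cannot be read in full.** The usage cell of the steroid row is cut off in the text available for this review, so its time window and exceptions are not fully visible. This limits the comparison of exceptions. It does not touch the threshold, which is in the medication cell and is complete.
- **Intent is clear.** Table 8, criterion 5 and Appendix 1 all agree, and Section 7.2's pointer to the tables leans towards Table 8. A careful reader would probably recognise a slip. This stands, and is the main reason the point is minor.
- **The affected group may be empty.** The planned total is at most 41 patients (Section 11), and no patient on sustained low-dose steroid can be identified from the documents. This also stands.
- **Harm is conjectural.** The number of sites is not given, and Section 7.2 requires the Principal Investigator to be told of any medication taken, which gives a chance to correct a misreading. This lowers the practical risk without making the two texts agree.

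**Conclusion.** The concern holds. Item 4 of Section 7.2.2 states the steroid threshold in the wrong direction, in current operative text. The conflict is confined to systemic doses up to and including 10 mg/day of prednisone or equivalent. After the stated exceptions, it matters only for sustained, non-replacement use unrelated to study treatment.

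This rests on two readings: that Table 8's threshold implies lower doses are acceptable, and that item 4 and Table 8 are meant to express the same rule. Both are well supported by their near-identical wording and by criterion 5 and Appendix 1. Confidence is high that the wording is wrong; whether any patient would be affected cannot be judged from the documents. It is a minor point about consistent conduct and deviation recording, with no bearing on the design, the dose-finding rules, the sample size or the analysis.

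**What to change.** In Section 7.2.2 item 4, delete the word *not*, so that the entry names systemic corticosteroids exceeding 10 mg/day of prednisone or equivalent, as Table 8 does. The existing exceptions can stay as they are. The cost is one word, which can be carried in the next amendment.
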